### **8.3. Screen Failures**

Subjects who sign and date the ICF but who fail to meet the inclusion and exclusion criteria are considered screen failures. Reason(s) for screen failure must be documented by the investigator and provided to the sponsor in a timely fashion. Subjects may be rescreened if the investigator considers rescreening appropriate. If a screened subject is not eligible for randomization, the primary reason for failure should be recorded on the applicable eCRF. The primary reason for screen failure should be recorded according to one of the following categories: did not meet inclusion criteria; did meet exclusion criteria; protocol violation or subject noncompliance (specify); lost to follow-up; withdrew consent; other (specify).

### **8.4. Subject Withdrawal Criteria**

A subject may withdraw consent at any point during the study. The investigator may discontinue a subject at any time if it is deemed medically appropriate, or for subject noncompliance with

study requirements. Subjects who withdraw will not be replaced. For subjects who are lost to follow-up (i.e., those subjects whose status is unclear because of failure to appear for study visits without stating an intention to withdraw), the investigator should document in the source documents steps taken to contact the subject. Subjects are to be withdrawn from the study if any of the following criteria are met:

- Occurrence of an AE, intercurrent illness, or laboratory abnormality which, in the opinion of the investigator, warrants the subject's permanent withdrawal from the study for subject safety.
- Withdrawal of informed consent
- Noncompliance with protocol procedures
- Lost to follow-up
- Pregnancy
- Study termination by the sponsor
- Other: COVID-19 site response

## **8.5. Methods of Birth Control**

Female subjects of childbearing potential who are sexually active with a male partner must practice one of the following methods of birth control during the study and for 30 days after the last dose of study drug.

- Oral or parenteral contraceptives
- Intrauterine device (either hormonal or non-hormonal type acceptable)
- Barrier (condom, contraceptive sponge, diaphragm, or cervical cap with spermicide)
- Abstinence

Females not of childbearing potential are defined as those who have been surgically sterilized (hysterectomy, bilateral oophorectomy, or tubal ligation) or who are post-menopausal (amenorrhea) for at least 2 years.

Female subjects of childbearing potential must have a negative pregnancy test at screening and Day 1.

Male subjects who are not surgically sterilized must agree to use an acceptable method of birth control and refrain from sexual activity with female sexual partners who do not use an acceptable method of birth control during the study and for 30 days after the last dose of study drug. Male subjects who are not surgically sterilized for at least 90 days prior to screening, and who are sexually active with a female partner, must agree to use barrier contraceptives (condom with spermicide) during the study and for 30 days after the last dose of study drug. Male subjects must also agree to refrain from sperm donation during the study and until 30 days after the last dose of study drug.

## 9. SCHEDULE OF PROCEDURES

### 9.1. Screening Period (Day -28 to -14)

- Informed consent form (ICF) must be signed before any protocol-directed procedures are performed. A separate ICF for optional pharmacogenomics (PGX) and PAX blood sampling will also be administered at the screening visit.
- Inclusion/exclusion criteria
- Demographics and habits (alcohol and/or illicit drug use, employment history, smoking history, and index traumatic event)
- Medical and psychiatric history (including non-pharmacologic interventions)
- PTSD diagnosis, according to DSM-5 (SCID-5-CT to exclude co-morbidities and CAPS-5 to diagnose PTSD)
- LEC-5 (part of PCL-5 with LEC-5 and Criterion A)
- S-STS (last month version)
- Vital sign measurements (after at least 5 minutes of rest, sitting or supine)
- Height (calculate BMI)
- Body weight (calculate BMI)
- PE
- ECG (after at least 5 minutes supine rest)
- Laboratory tests:
  - Clinical chemistry (calculate estimated creatinine clearance)
  - Hematology
  - HIV, hepatitis B surface antigen, hepatitis C antibody
  - Serum pregnancy test for women of childbearing potential
  - Drug and alcohol screen (serum)
  - Urinalysis
- Clinical measures:
  - CAPS-5
  - PCL-5 (last month version)
  - HADS
  - CGI-S
  - PSQI
  - PSQI-A

○ [REDACTED]

- Prior and concomitant medications
- SAEs (collection begins after ICF signed)

### **9.2. Day -14 (±3 days)**

Subjects who meet eligibility criteria according to the PCL-5 ( $\geq 38$ ), SCID-5-CT, and CAPS-5 (total score  $\geq 30$ ) at screening will complete a SAFER remote phone interview. Those subjects confirmed to have met the study diagnostic and selection criteria as determined during the SAFER interview are then eligible to proceed in the study.

### **9.3. Stage 1: Day 1**

- Medical and psychiatric history updates (if applicable)
- Inclusion/exclusion criteria
- S-STS (since last visit version)
- Vital signs (after at least 5 minutes of rest, sitting or supine)
- Body weight
- ECG (after at least 5 minutes supine rest)
- Concomitant medications
- Laboratory tests
  - Clinical chemistry (fasted)
  - Hematology
  - [REDACTED]
  - [REDACTED]
  - Pregnancy test (urine) for women of childbearing potential
  - Drug (urine) and alcohol screen (breathalyzer)
  - Urinalysis
- Clinical measures (all measures except for CAPS-5 are not required if last measurement is within 14 days prior to Day 1)
  - CAPS-5
  - PCL-5
  - HADS
  - CGI-S
  - PSQI
  - PSQI-A

- [REDACTED]
- DES-II
- BAC-Symbol Coding
- Randomization
- Study drug dispensing, dose administration (in clinic and after completion of above-noted study procedures), and compliance monitoring
  - Medication adherence and reminder system training
- AEs (serious and non-serious)

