
Investigational product, dosage and mode of administration: NYX-783 50-mg oral capsule(s) or matching placebo There are 3 treatment arms:
 

• NYX-783 50 mg QD

• NYX-783 10 mg QD

• Placebo QD

Participant Duration: (approximately 12 weeks total duration)
 

• Screening: Up to 21 days before randomization

• 8-week treatment period: 4 weeks of NYX-783 50 mg QD or 10 mg QD and 4 weeks of placebo or 8 weeks of placebo followed by a one-week post-therapy safety follow up period

○ Stage 1: 4 weeks

○ Stage 2: 4 weeks

Criteria for evaluation:

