Abbreviations: BAC-Symbol Coding = Symbol Coding from the Brief Assessment of Cognition; CAPS-5 = Clinician Administered PTSD Scale for DSM-5; [REDACTED] CGI-S = Clinical Global Impression – Severity; DES-II = Dissociative Experiences Scale-II; DNA = Deoxyribonucleic acid; ECG = electrocardiogram; HADS = Hospital Anxiety and Depression Scale; HIV = human immunodeficiency virus; LEC-5 = Life Events Checklist for DSM-5; [REDACTED] PCL-5 = PTSD Checklist for DSM-5; [REDACTED] PSQI = Pittsburgh Sleep Quality Index; PSQI-A = Pittsburgh Sleep Quality Index Addendum; PTSD = Post-Traumatic Stress Disorder; SCID-5-CT = Structured Clinical Interview for DSM-5 (Clinical Trials Version); [REDACTED]; S-STIS = Sheehan Suicidality Tracking Scale.

- a) Visit window is ± 3 days.
- b) Includes alcohol or illicit drug use history, employment status, smoking history, and index traumatic event.
- c) Collect vital signs after at least 5 minutes of rest, seated or supine.
- d) ECG after at least 5 minutes supine rest.
- e) Include body mass index calculation.
- f) Subjects use smartphone video application monitoring. Investigative site personnel calculate compliance and document accountability via capsule count/blister package inspection.
- g) Serious Adverse Event (SAE) reporting begins at time of informed consent and continues until 30 days after the last dose of study drug. Non-serious AE collection commences with the time of first dose of study drug until last day of subject participation in the study.
- h) Serum sample.
- i) Urine sample or breathalyzer (alcohol screen).
- j) Via phone.
- k) Doses are to be administered at the clinic on Day1 (after completing other procedures) then on an outpatient basis.

- l) Stage 2 dosing begins on the day after the Week 4 visit.
- m) Includes concurrent medical and psychiatric history.
- n) [REDACTED]
- o) Use interactive response technology for study drug dispensing.
- p) 7 days post-therapy.
- q) Clinical labs should be fasted except for screening.
- r) Only if required for adverse event follow-up.
- s) Rating based on the past month
- t) Rating based on the past week
- u) Use “since last visit” version after screening.
- v) Women of childbearing potential.
- w) Remote visit (optional. Only if necessary, due to COVID-19 health emergency)
- x) Visit window is  $\pm 7$  days.

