#### **12.2.3. PTSD Checklist for DSM-5 (PCL-5)**

The PCL-5 is a 20-item self-report measure that assesses PTSD symptoms experienced over the last week or month according to DSM-5 criteria. Items assess symptoms across 4 symptom clusters of PTSD (re-experiencing, negative mood, avoidance, and hyperarousal) on a 0-4 point Likert scale. Total scores range from 0-80. The “since last week” version should be used after screening.

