## 6. General Issues for Statistical Analysis

### 6.1. Statistical Definitions and Algorithms

#### 6.1.1. Baseline

The last non-missing observation recorded prior to the first dose of study drug (NYX-783 or placebo) will be used as the baseline observation for all calculations of change from baseline for Stage 1 data. For purposes of safety evaluation, subjects that are re-randomized in Week 4, the last non-missing observation before Week 4 will be used as baseline for Stage 2 data, with exception of groups [4] and [7] as referenced in [Figure 1](#). Changes from baseline for these groups will be based on the Stage 1 baseline given their study intervention remained unchanged.

For purposes of efficacy analyses, baseline values for Stage 2 data within all groups [4], [5], [6], [7], [8], [9], [10], and [11] will be based on the last assessment prior to first dose of study drug in Stage 2.

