## 8.3. Exploratory Efficacy Analyses

### 8.3.5. Subgroup Analyses

The primary efficacy endpoint will be described on the following subgroups

1. Gender
2. Race (White, Non-white)
3. Time Since Trauma ( $\leq$  median and  $>$  median), date of trauma from medical

history where mhterm equals PTSD, POST TRAUMATIC STRESS DISORDER

4. Marital Status (Married, Not Married)
5. Trauma type(Sexual Abuse (from medical history where preferred term in “Sexual Abuse”, “Victim of Sexual Abuse) vs. other)
6. Taken Pain Medication during study () at any point in the study (Yes, No). The list of concomitant medications will be reviewed prior to database lock and pain medications of interest will be identified for this analysis.
7. PSQI Sleeping Status (Good Sleeper total score <=5, Poor Sleeper total score >5) at baseline (Day 1 only)
8. HADS-A and HADS-D Score categories (normal (0-7), borderline abnormal (8-10) and abnormal (>=11))
9. Subjects with and without AEs of interest at any point during the study (Yes, No)
10. Subjects with high avoidance scores- Subjects with score 3,4 in avoidance categories of CAPS5 Q6,7 or distant from other people, Q13.

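### Protocol 9.3 allows the Day 1 PCL-5 to be skipped, so a past-month screening score can become the Stage 1 baseline for past-week follow-up scores

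*Protocol*

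**What the plan says.** **The waiver.** Protocol 9.3 (Stage 1: Day 1) heads its list of clinical measures with "all measures except for CAPS-5 are not required if last measurement is within 14 days prior to Day 1".

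**No waiver elsewhere.** The Synopsis (Treatment Period) has both CAPS-5 and PCL-5 assessed on Day 1. Table 4 marks PCL-5 on Day 1 with no footnote that allows an omission.

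**Recall period.** Protocol 9.1 lists the last-month form of the PCL-5 at screening, and Table 4 footnote s for that visit reads "Rating based on the past month". From Day 1 on, Table 4 gives a past-week rating (footnote t). Protocol 12.2.3 agrees: "The “since last week” version should be used after screening".

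**Baseline.** For Stage 1, SAP 6.1.1 uses "The last non-missing observation recorded prior to the first dose of study drug". It sets no condition on recall version.

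**Use of the baseline.** SAP 8.2 analyses PCL-5 with the primary-endpoint methods and its own baseline as covariate. SAP 6.1.4 defines PCL-5 response as a 10-point fall from the 6.1.1 baseline at the end of each stage.

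**Screening window.** The Synopsis (Screening period), Protocol 7.1, Table 4 and Protocol 9.1 give Day -28 to -14. SAP Table 1 and the Protocol table of contents give Day -21 to -7. The Synopsis entry on participant duration reads "Screening: Up to 21 days before randomization", and the opening of Protocol 7.1 gives 3 weeks.

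**The concern.** A site that follows 9.3 departs from Table 4, and a site that follows Table 4 never uses the waiver. The documents therefore disagree on whether a Day 1 PCL-5 is required.

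Where the waiver is used, the baseline differs from every later score in two ways. It covers a month rather than a week. It is also the score that had to reach 38 for entry, so it is expected to sit above an unselected repeat in the same person.

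PCL-5 is a secondary efficacy endpoint. Because SAP 8.2 carries over the methods of SAP 8.1.1, its Stage 1 effect has weight 0.6. At stake are the within-arm Stage 1 change, the Stage 1 responder rate and the usefulness of the baseline covariate.

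**Working it through.** The plan gives no figure for this point, so there is none to reproduce.

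**1. Which measures the waiver can reach.** It covers only the clinical-measures list in 9.3. S-STS, vital signs, ECG and laboratory tests are outside it. DES-II and BAC Symbol Coding have no screening value in Table 4, so there is nothing to carry forward. That leaves PCL-5, HADS, CGI-S, PSQI and PSQI-A. HADS carries the past-week footnote throughout, and PSQI and PSQI-A ask about one month (Protocol 12.2.5, 12.2.6). Only PCL-5 changes recall version.

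**2. Which screening days qualify.** Count the days in each window that are at most 14 days before Day 1. The documents do not say whether there is a Day 0, so both counts are shown.

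| Window | No Day 0 | With a Day 0 |
|---|---|---|
| Day -28 to -14 (15 days) | 1 (Day -14) | 0 |
| Day -21 to -7 (15 days) | 8 (Day -14 to -7) | 7 (Day -13 to -7) |

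These are calendar days, not subjects.

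**3. Effect of selection alone.** The assumptions are not in the documents: PCL-5 normal with mean μ of 45 or 50, SD 13, correlation ρ of 0.6 or 0.8 between any two occasions, selection at 38 or more, no true change and no recall-period effect.

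Expected excess of screening over Day 1 = (1 − ρ) × SD × λ, where λ = φ(a)/(1 − Φ(a)) and a = (38 − μ)/SD.

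- μ = 45: a = −0.54, λ = 0.490. Excess = 0.4 × 13 × 0.490 = 2.5 points (ρ = 0.6), or 0.2 × 13 × 0.490 = 1.3 (ρ = 0.8).
- μ = 50: a = −0.92, λ = 0.317. Excess = 1.6 points (ρ = 0.6), or 0.8 (ρ = 0.8).

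The chance of an apparent 10-point fall at Week 4 was simulated for a screening baseline. For a Day 1 baseline it is 1 − Φ(10 / (13√(2(1 − ρ)))).

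| μ, ρ | Screening baseline | Day 1 baseline | Difference (points) |
|---|---|---|---|
| 45, 0.6 | 24.9% | 19.5% | 5.4 |
| 45, 0.8 | 13.8% | 11.2% | 2.6 |
| 50, 0.6 | 22.6% | 19.5% | 3.1 |
| 50, 0.8 | 12.7% | 11.2% | 1.5 |

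Selection therefore adds about 2 to 5 percentage points, in waived subjects only.

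**4. Effect of the recall period.** The documents give no size for it. Assume that past-month scores run m = 2 to 6 points above past-week scores, with a true mean fall of 8 and SD of change 12. The response rate is 1 − Φ((10 − 8 − m)/12). It is 43% with m = 0, 50% with m = 2 and 63% with m = 6. The mean fall is overstated by m.

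**5. Effect on the treatment contrast.** The screening score is recorded before randomisation, and so is any decision to skip the Day 1 form if 9.3 is followed in its listed order. Waived subjects are then expected in equal proportion in each arm. A shift of m in a fraction f of subjects moves each arm's mean change by f × m, and the expected difference between arms is unchanged. What remains is extra variance and a covariate that mixes two instruments.

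**The case against.** The strongest reply is that the waiver hardly operates. The current Protocol's visit text puts screening at Day -28 to -14, with the SAFER interview around Day -14. A subject screened on Day -14 exactly is the only one who could use it, and Protocol 12.4.5 allows screening to run longer. The waiver is also permissive, and a schedule table need not repeat every condition in the visit text. This stands as a limit on reach. It does not remove the defect: the shorter window remains in SAP Table 1 and the Protocol contents list, and nothing shows how many analysed subjects were screened under which window.

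Several stronger readings are tempting but not supported:

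- **Biased PCL-5 treatment effect.** A reader might infer this from the inflated change. The baseline precedes randomisation, so the inflation is expected equally in all arms.
- **More than half of subjects affected.** The 8 of 15 figure counts permitted days under a window that the current visit text does not use.
- **13 to 25% false responders.** That is the gross rate with a screening baseline. On the same assumptions a proper Day 1 baseline already gives 11 to 20%.
- **Loss of subjects from the sleep subgroup.** SAP 8.3.5 item 7 takes PSQI status "at baseline (Day 1 only". A reader might infer that a waived subject has no value. The phrase can equally mean the Stage 1 rather than the Stage 2 baseline, and then the screening PSQI serves. The subgroup summary is exploratory in any case.

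**Conclusion.** The conflict between Protocol 9.3 and the Synopsis and Table 4 is established from the text. So is the route by which a past-month PCL-5 becomes the Stage 1 baseline. Both hold without any assumed number.

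The consequence is modest. It is confined to Stage 1 of a secondary endpoint, in an unknown number of subjects that should be small if the current window was followed. CAPS-5 is excluded from the waiver, so the primary endpoint is untouched. Stage 2 efficacy baselines come from assessments taken after screening, which are past-week. Within waived subjects, mean change and 10-point response are overstated in every arm: by about 2 to 5 percentage points of response from selection on the assumed mean, SD and correlation, plus a recall-period effect whose size the documents do not give. The covariate also loses some precision.

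**What to change.** 1. **Protocol 9.3:** remove PCL-5 from the waiver, or delete the waiver, so that the past-week PCL-5 is always taken on Day 1 as Table 4 shows.
2. **Screening windows:** reconcile the Protocol visit text, the Synopsis duration entry, the opening of Protocol 7.1, the table of contents and SAP Table 1.
3. **SAP 6.1.1:** state that the PCL-5 Stage 1 baseline is the Day 1 past-week score.
4. **Subjects already enrolled without a Day 1 PCL-5:** keep them in the ITT analysis, with the screening score as a flagged fallback, because a change-from-baseline model drops anyone with no baseline. Report their number by arm, and run a sensitivity analysis of PCL-5 change and response without them.

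Leaving these subjects out of the main analysis would depart from ITT to cure an imprecision that is not expected to differ between arms. With 156 subjects at 4:1:1, each active arm has 156/6 = 26 in Stage 1, so exclusions would be costly.

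The cost is a few minutes of self-report on Day 1 for subjects who would have skipped it, short edits to the Protocol and SAP, and one extra sensitivity analysis. If enrolment is complete, items 3 and 4 can still be done before unblinding.

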#### **9.4. Week 2, Day 14 ( $\pm 7$ days)**

- S-STS (since last visit version)
- Vital sign measurements (after at least 5 minutes of rest, sitting or supine)
- Body weight
- Laboratory tests: clinical chemistry (fasted)
- Clinical outcome measures
  - CAPS-5
  - PCL-5
  - HADS
  - PSQI
  - PSQI-A
  - CGI-S
- Study drug accountability, compliance review, and dispensing
  - Medication adherence and reminder system review
- Concomitant medications
- AEs (serious and non-serious)

#### **9.5. Stage 2: Week 4, Day 28 ( $\pm 3$ days)**

Study drug (including extra kit) dispensed in Stage 1 may not be re-dispensed and/or administered in Stage 2.

- S-STS (since last visit version)
- Vital signs (after at least 5 minutes of rest, sitting or supine)
- Body weight
- PE
- ECG (after at least 5 minutes supine rest)
- Laboratory tests

- Clinical chemistry (fasted)
- Hematology
- Plasma concentration blood sample
- RNA (miRNA, mRNA) PAXgene® blood sample (optional)
- Pregnancy test (urine) for women of childbearing potential
- Drug (urine) and alcohol screen (breathalyzer)
- Urinalysis
- Clinical measures
  - CAPS-5
  - PCL-5
  - HADS
  - CGI-S
  - PSQI
  - PSQI-A
  - BAC-Symbol Coding
  - ██████
  - DES-II
- Randomization (for Stage 2)
- Study drug accountability, compliance review, and dispensing (for next day dosing)
  - Medication adherence and reminder system review
- Concomitant medications
- AEs (serious and non-serious)

### **9.6. Week 6, Day 42 (±7 days)**

- S-STS (since last visit version)
- Vital signs (after at least 5 minutes of rest, sitting or supine)
- Body weight
- Laboratory tests: clinical chemistry (fasted)
- Clinical outcome measures
  - CAPS-5
  - PCL-5
  - HADS

- PSQI
- PSQI-A
- CGI-S
- Study drug accountability, compliance review, and dispensing
  - Medication adherence and reminder system review
- Concomitant medications
- AEs (serious and non-serious)

**9.7. Week 8, Day 56 (±3 days)**

- S-STIS (since last visit version)
- Vital signs (after at least 5 minutes of rest, sitting or supine)
- Body weight
- PE
- ECG (after at least 5 minutes supine rest)
- Laboratory tests
  - Clinical chemistry (fasted)
  - Hematology
  - Plasma concentration blood sample
  - [REDACTED]
  - Drug and alcohol screen (serum)
  - Pregnancy test (urine) for women of childbearing potential
  - Urinalysis
- Clinical outcome measures
  - CAPS-5
  - PCL-5
  - HADS
  - CGI-S
  - PSQI
  - PSQI-A
  - BAC-Symbol Coding
  - [REDACTED]
  - DES-II
  - [REDACTED]

- Study drug accountability and compliance review
  - Medication adherence system review and retrieval of device (if applicable)
- Concomitant medications
- AEs (serious and non-serious)

### **9.8. Early Termination Visit**

- S-STS (since last visit version)
- Vital signs (after at least 5 minutes of rest, sitting or supine)
- Body weight
- PE
- ECG (after at least 5 minutes supine rest)
- Laboratory tests
  - Clinical chemistry (fasted)
  - Hematology
  - Plasma concentration blood sample
  - [REDACTED]
  - Drug and alcohol screen (serum)
  - Pregnancy test (urine) for women of childbearing potential
  - Urinalysis
- Clinical measures
  - CAPS-5
  - PCL-5
  - HADS
  - CGI-S
  - PSQI
  - PSQI-A
  - BAC-Symbol Coding
  - [REDACTED]
  - DES-II
  - [REDACTED]
- Study drug accountability and compliance review
  - Medication adherence system review and device retrieval (if applicable)
- Concomitant medications

- AEs (serious and non-serious)

### **9.9. Safety Follow-up Visit (7 days post-therapy $\pm$ 3 days)**

The following safety assessments are to be performed only if required for AE follow-up:

- Vital signs (after at least 5 minutes of rest, sitting or supine)
- Body weight
- PE
- ECG (after at least 5 minutes supine rest)
- Laboratory tests
  - Clinical chemistry (fasted)
  - Hematology
  - Urinalysis

The following assessments are to be performed for all subjects at this visit:

- Concomitant medications
- AEs (serious and non-serious)

